APPENDIX I summarizes the study timeline and measurements.

3.4.1 Cogstate Brief Battery (CBB)

The Cogstate Brief Battery (<https://www.cogstate.com>) is a computer-based cognitive test extensively validated against standard neuropsychological batteries in cognitively normal older adults, as well as in patients with cognitive impairment, in the community and in different clinical contexts, both in a clinician/researcher-supervised manner, and in an unsupervised fashion (i.e., through an internet-based self-administration, at home). ⁸⁻¹⁰ It has been used also in the perioperative setting, showing equivalent or greater reliability, and greater sensitivity than conventional batteries.^{11 12} Moreover, In addition to proof of feasibility and acceptability even with older patients with some baseline cognitive impairment, its advantages are short duration (about 15 min), small practice effects (even with monthly assessments), and no ceiling effects.^{8 13} It consists of four tasks (*Detection Task*, *Identification Task*, *Learning Task*, and *One-Back Task*) designed to assess psychomotor function, attention, working memory, and visual learning.¹³ Each task utilizes stimuli in the form of playing cards. Stimuli characteristics (e.g.,

color, suit) are manipulated based on the requirements of each task. The primary performance measure for the *Detection* and *Identification* tasks is reaction time in milliseconds (speed), which is usually normalized using a logarithmic base 10 (\log_{10}) transformation. The primary performance measure for the *Learning* and *One-Back* tasks is the proportion of correct answers (accuracy), which is usually normalized using an arcsine square-root transformation.

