Based on industry web standards, the Cogstate system will communicate with the McMaster system through an Application Programming Interface (API), to generate user- and visit- specific links. The CBB will be host in a McMaster webpage, in a seamless fashion for the participant, who will be directed into the Cogstate application when they start the assessment, and then back to the hosting website upon completion of the tests. The CBB will present each cognitive test to the subject following a self-paced training test until valid cognitive data is provided, enabling testing without supervision. Subjects will receive a simple message at the end of their testing session indicating next steps. A detailed report with cognitive data will not be provided to subjects. For the purpose of this study, a support person will be allowed to attend the self-administration of the CBB. This will be established at the enrolment for each participant, and the participant will be instructed to self-administer the CBB under the same conditions at every assessment over time.

After 1-5 days from the initial recruitment and training session, each participant will self-administer the cognitive testing once, and then every month (i.e. 30 days, ± 1 week) until their surgery is performed. We expect that each participant will have at least 2 assessments before surgery. Participants will then self-administer the CBB 1 month, 3 months, 6 months, and 12 months after surgery.

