3.5 Sample size

The slowdown of the operating rooms due to COVID-19 started in mid-March, and it will last at least until the end of June or July at the participating sites. We expect to recruit 330 participants between May and August 2020. This sample size will be sufficient to test our primary hypothesis that, on average, in our population, the cognitive performance at 6 months after surgery will be worse, in a clinically significant way, compared to what we would expect based on the preoperative trajectory. We will base our primary hypothesis on the performance at the *One-Back Task (OBK)* of the CBB, at 6 months after surgery. The *OBK* assesses working memory, which is a cognitive domain often found altered in the context of postoperative cognitive dysfunction. It uses a well-validated n-back paradigm with stimuli from playing cards. The subject is asked whether the card displayed in the center of the screen is the same as the card presented immediately before. The subject responds by pressing the “yes” or “no” key. The primary outcome variable for this test is accuracy of correct response, normalized using an arcsine square-root transformation. In **APPENDIX II** we provide a table summarizing the clinical relevance of the test and its results, with data on the difference in performance between healthy older adults, and older adults with mild cognitive impairment (MCI) or dementia based on standardized neuropsychological assessment.^{13 19} Based on the literature, a typical score of healthy older adults is 1.35; the average difference, at one time point, in the *OBK* score, between healthy older adults and older adults with mild cognitive impairment (MCI), and older adults with dementia, is, respectively, 0.07 and 0.17.^{13 19} We hypothesize that in our study population we will see a preoperative trajectory, which, if it continued, unchanged, after surgery (H_0), would lead to an average decrease in OBK score of 0.009 over 6 months. This is still consistent with a decline over time compared with what we would expect on average in a healthy older population.^{13 19} Our hypothesis (H_1) is that surgery will change the preoperative trajectory so that at 6 months after surgery we will instead see an average decrease, compared with right before surgery, of 0.035 (which would correspond to the average change in a hypothetical population in which 40% of subjects experience a decline of at least 0.07, 50% no

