impact of surgery can last as long as one year,² we will repeat the analysis including also the change between 6 and 12 months after surgery. In our regression models, we will use estimates of error variance obtained from bootstrap techniques using 1000 bootstrap samples. We will analyze the performance at each task separately, and then combining the 4 scores into one unique measure of performance. We will explore whether clinically significant changes have occurred at any time point. There is no standard definition for what is a clinically significant perioperative decline across different tests.^{24 25} In addition to the change as defined in our sample size calculation (i.e. a change in score equal to or greater than the average difference in scores between a healthy older adult and a subject with MCI), we will consider also 2 most commonly adopted definitions, i.e. 1) a change of $\geq 20\%$ in test scores,²⁶ and 2) a reliable change index (RCI) of ≥ 1.65 . The RCI is an index commonly used in neuropsychology,²⁷ and also in studies using the CBB,¹³ calculated by dividing the individual's test-retest difference score by the standard error of that difference score, and can be interpreted as a standard Z score. The cut-off of RCI=1.65 is the point beyond which 5% of the values from the normal sample population will fall (i.e. $P<0.05$, one tailed test). We will compare the performance scores at each time point with the preceding time points, and evaluate the changes based upon these criteria. We will provide the number and percentage of patients experiencing a cognitive decline based on these definitions at each of the segments of the observation period. We will also compare our study population data with existing age-stratified normative data for the CBB.²⁸

In our primary analyses, we will include only patients who completed ≥ 2 assessments preoperatively and ≥ 3 assessments (i.e. 1, 3, and 6 months) postoperatively. Secondarily, we will repeat our analysis dealing with missing data 1) through multiple imputation techniques; and 2) using a method of evidence-informed data imputation, previously implemented in our studies, which takes onto account the reason for the missing data.³

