3.6.2 Secondary Analyses

We will explore whether the effect of surgery on cognitive trajectories differ based on baseline patient characteristics, including age, type of surgery, cognitive performance at baseline, comorbidities, mobility, GDS and pain score. This will be done studying the interaction of these covariates with the components of the interrupted time analysis. The interrupted time series approach as described assumes linearity and constancy of the preoperative trend when projected postoperatively. We will evaluate the validity of these assumptions exploring the association of changes in cognitive performance with intercurrent events other than the index surgery, for the long-term effects.

With a similar approach as for the cognitive performance, we will study the perioperative trajectories of patient physical function/mobility (as indicated by the LLFDI-FC and the life space mobility questions), depressive symptoms (as indicated by the GDS), and of pain (as indicated by the NPRS). We will also explore whether the time-dependent LLFDI-FC, GDS and NPRS scores are associated with the time-dependent cognitive scores.

STATA software, version 15, will be used for the analyses.

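### Tests are monthly before surgery and sparser after it, but the primary model runs on time alone, so a steady practice gain g per test creates a false 6-month shortfall of about 3g to 4g

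*Combined protocol and SAP*

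**What the plan says.** Before surgery, section 3.4.1 has participants take the battery once and "then every month (i.e. 30 days, ± 1 week) until their surgery is performed". After surgery the rule becomes: "Participants will then self-administer the CBB 1 month, 3 months, 6 months, and 12 months after surgery". Appendix I shows the same schedule. Section 3.4.1 adds "We expect that each participant will have at least 2 assessments before surgery", and section 3.6.1 limits the primary analysis to "only patients who completed ≥ 2 assessments preoperatively and ≥ 3 assessments (i.e. 1, 3, and 6 months) postoperatively".

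The primary hypothesis in section 3.5 is that "the cognitive performance at 6 months after surgery will be worse, in a clinically significant way, compared to what we would expect" from the preoperative trajectory, measured on the OBK. The model in section 3.6.1 has a preoperative slope, a level change at surgery and a slope change. A second model allows separate slopes between the postoperative visits. Both are functions of time.

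On practice, section 3.4.1 claims "small practice effects (even with monthly assessments" for the battery and gives no number. Section 3.6.2 acknowledges that the approach "assumes linearity and constancy of the preoperative trend when projected postoperatively", and examines this only through intercurrent events other than the index surgery.

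**The concern.** A practice gain accrues with each test taken, whereas the model counts months. Before surgery the two advance together, at about one test per month. After surgery they separate: the gaps are 1 to 3, 3 to 6 and 6 to 12 months. A slope learned under monthly testing is projected into a period of sparser testing, and the missing practice looks like lost performance. The testing rule changes at the same event as the exposure, so a model with time terms alone cannot separate the two.

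The primary 6-month contrast is at stake. For a positive steady gain the bias lies in the direction of the study hypothesis, and a larger sample does not reduce it. The plan has no test-number term and no unoperated group tested on the same schedule. The reliable change index, as described in section 3.6.1, has no practice correction.

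**Working it through.** **Inputs.** The test schedule is from section 3.4.1. Section 3.5 gives the expected 6-month changes of -0.009 (H0) and -0.035 (H1), SD 0.16, two-sided alpha 0.05, 80% power and 10% attrition. The gain per test, g, is not in the documents; 0.001 to 0.010 OBK units is an assumption. The last preoperative test is taken to fall u months before surgery, with u between 0 and 1.

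**1. The plan's own figure.** The planned difference is 0.035 - 0.009 = 0.026. Then n = (0.16 × (1.960 + 0.842) / 0.026)² = 297.2, and 297.2 / 0.90 = 330.3. The stated 330 is reproduced, so 0.026 is the yardstick.

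**2. Hand count, steady gain, no surgery effect.**
- Gain projected from the last preoperative test to month 6: (6 + u)g.
- Gain realised from the tests at months 1, 3 and 6: 3g.
- Shortfall: (6 + u)g - 3g = (3 + u)g, that is 3g to 4g.
- At month 12: (12 + u)g - 4g = (8 + u)g, that is 8g to 9g.

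**3. The section 3.6.1 model.** It was fitted with patient fixed effects to noise-free data with a steady gain and no surgery effect, using 2 to 4 preoperative tests per patient. The 6-month contrast is level change + 6 × slope change.

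| Last test before surgery | Level change | Slope change per month | 6-month contrast |
|---|---|---|---|
| u = 0 | +0.68g | -0.605g | -2.95g |
| u = 1 | -0.32g | -0.605g | -3.95g |
| u spread over 0 to 1 | +0.25g | -0.56g | -3.1g |

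With an assumed mix of 2 to 5 preoperative tests (40/30/20/10%) and u spread over 0 to 1, the contrast is about -3.2g. If postoperative tests were also monthly, the hand-count shortfall would fall to ug.

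**4. Size against 0.026.**

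| Assumed g | Shortfall at month 6 | Share of 0.026 |
|---|---|---|
| 0.001 | 0.003 to 0.004 | 12% to 15% |
| 0.002 | 0.006 to 0.008 | 23% to 31% |
| 0.005 | 0.015 to 0.020 | 58% to 77% |
| 0.010 | 0.030 to 0.040 | 115% to 154% |

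The shortfall equals 0.026 when g is 0.026/4 = 0.0065 to 0.026/3 = 0.0087, which is 4% to 5% of the SD of 0.16.

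**5. Chance of a false significant result.** With the sample-size section's own standard error, 0.16/√297 = 0.0093, it is 10% to 14% at g = 0.002 and 37% to 58% at g = 0.005. That standard error ignores uncertainty in the projected slope. With that uncertainty included (assumed residual SD 0.08 to 0.12), it is 7% to 11% at g = 0.005 and 15% to 31% at g = 0.010.

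**6. Front-loaded gain.** If the whole gain comes at the second test, the contrast is about -2.1 times that gain, and still -2.0 times with monthly postoperative tests. If the gain is proportional to the log of test number (the 2-to-5 mix), the contrast is about -2.6 per doubling, and about -1.6 of it (62%) remains with monthly postoperative tests. Most of this bias comes from extrapolating early gain, not from the spacing.

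**7. Test-number terms (same 2-to-5 mix).** A linear term removes a steady gain exactly, but makes the standard error of the contrast about 2.2 times larger. A log term makes it about 1.5 times larger and leaves about four fifths of a steady gain (about -3.2g becomes -2.5g).

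**The case against.** The strongest objection is that the key input is missing. The protocol describes practice effects as small even with monthly testing. At g = 0.001 the bias is only 0.003 to 0.004. At the other end, month 6 is the fifth to eighth test, so a steady 0.008 would add 0.032 to 0.056 by then. That is 46% to 80% of the 0.07 difference between healthy older adults and those with mild cognitive impairment in Appendix II, and is hard to call small. This stands: the size is unknown and the whole assumed range has to be shown.

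The plan also has partial mitigations: a training videoconference, a self-paced practice run before each task, and the model with separate postoperative slopes. The first two may blunt early learning. None removes a steady per-test gain, and the separate slopes are still slopes on time.

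A reader might infer more than the documents support:
- **That the bias always favours the study hypothesis.** It does for the fitted 6-month contrast and the slope change under a positive steady gain. The level change, which section 3.6.1 attributes to surgery, is biased by about +0.25g on average, the other way. If the sample-size test were run literally against a fixed -0.009, practice would hide a decline. It would also hide decline in the 20% and reliable-change counts, which compare scores directly.
- **That spacing changes sharply at surgery.** The gap across surgery is only about 1 to 2 months; the clear widening comes after month 1.
- **That any practice gain is a spacing problem.** For front-loaded gain, most of the bias would remain with unchanged spacing.
- **That raw scores would fall.** They would still rise by 3g; the decline is relative to the projection.

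**Conclusion.** The concern holds for the 6-month contrast and the slope change. With a positive steady gain and no surgery effect, the planned model gives a false shortfall of about 3g to 4g at month 6, and 8g to 9g by hand count at month 12. Over the assumed 0.001 to 0.010 per test, the 6-month figure runs from about 0.003 to 0.04, which spans negligible to larger than the planned 0.026. This rests on a gain that does not plateau, on monthly preoperative testing with the last test within a month of surgery, and on the time-only model in section 3.6.1. The documents do not show that the planned result would be false, or even that the bias would be large. They do leave the 6-month shortfall without any check that separates surgery from less frequent testing.

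**What to change.** Add to section 3.6.1 a pre-specified, reported sensitivity analysis of the 6-month OBK contrast, in two parts.

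(a) Re-estimate the contrast with a test-number term beside the time terms, once in log form and once in linear form.

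(b) Subtract the practice bias over a stated range of gain per test, for example 0 to 0.010. Compute the multiplier from the test dates actually observed instead of fixing it at 3.2, because it depends on the number and timing of preoperative tests. Report the gain at which the conclusion disappears.

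Describe the 6-month shortfall as an effect of surgery only with this range beside it. A rule that the effect must survive every model is not warranted. The objectives are to describe and explore, and a sensitivity model with a standard error of about 0.03 has little power against 0.026.

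The cost is SAP wording and a few extra models, with no change to visits. The downside is precision: the test-number models are less precise by the factors in step 7, because test number and time are almost collinear before surgery. The log term alone removes only about a fifth of a steady gain, so part (b) is needed as well.

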3.4.2 Changes in activities and participation since COVID-19 questionnaire

Appendix III shows the questionnaire exploring changes in activities and participation since COVID-19. The questionnaire has been developed in the context of a survey study that is being conducted by investigators at the McMaster Institute for Research on Aging (MIRA) & Labarge Centre for Mobility in Aging (LCMA). In the MIRA/LCMA survey the questionnaire is administered, by telephone, to 500 community-dwelling older adults living in Greater Hamilton area, identified through random sampling based on census. In the Co-TELE-SURGE the questionnaire will be administered by the research personnel only once, i.e. at baseline, to collect data on the change in activities and participation experienced by the subject after the social distancing was imposed to face the COVID-19 pandemic, which, for the participants in our study temporally coincided with the change to their surgical plan.

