2. OBJECTIVES

The primary objectives of our project are to describe perioperative cognitive trajectories of older patients whose elective noncardiac surgery has been deferred because of the COVID-19 emergency, and explore the intra-individual changes in these trajectories from before to after surgery, through periodic remote self-administered cognitive testing.

In the same study population, we will also have the following secondary objectives:

- to describe the perioperative trajectories in mobility/physical function, depressive symptoms and pain, and explore their association with the trajectories in cognitive performance, before and after surgery;
- to describe the change in activities and participation after the COVID-19 and social distancing started, in our study population, compared to a random sample of community-dwelling persons, 65 years old or older, in order to identify the additional impact of surgery deferral. We will pursue this secondary objective comparing our data with the results of an ongoing cross-sectional survey across community-dwelling older adults living in Greater Hamilton areas.

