3.2 Study population

We expect to include 330 patients aged 65 years or older, scheduled for their noncardiac elective surgery whose surgery has been or will be deferred due to the slowdown of the operating rooms during the COVID-19 emergency at the Hamilton Health Science (HHS), St. Joseph's Healthcare Hamilton (SJHH), Woodstock General Hospital, London Health Sciences

Centre, Kingston General Hospital, Memorial University of Newfoundland, University of Saskatchewan, and University of Alberta.

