3.2.1 Inclusion criteria

1. age 65 years or greater
2. patient scheduled to perform noncardiac elective surgery expected to require at least an overnight stay in hospital after surgery
3. surgery deferred, with a known or probable surgery date in ≥6 weeks
4. informed consent provided

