change, and 10% an improvement of 0.07). Based on a test of comparison of means in one sample, with an alpha error of 0.05 (2-tailed), and a standard deviation for the OBK score of 0.16,¹³ to enrol 330 subjects will be sufficient to test our hypothesis with 80% of power, even in case of an attrition rate as high as 10%.

Recruiting 330 participants is a feasible goal based on the current status of knowledge about the COVID-19 contingency plan. The lockdown of the operating rooms started in March and will last at least until the end of June, or longer, depending on the participating site. During the lockdown, we expect to be able to enroll at least 120 participants at McMaster sites, and 30-50 participants at each of the other participating sites. Even when the operating rooms will reopen to more elective surgeries in the next months, this will happen slowly, so that we expect a carryover of the lockdown at least until the end of the summer. Moreover, it is projected that, if countries increase their normal surgical volume by 20% post-pandemic, it would take a median 45 weeks to clear the backlog of operations resulting from COVID-19 disruption.²⁰ Therefore should we see a recruitment rate slower than expected, for any reason, we will extend our recruitment period to beyond the summer.

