APPENDIX III. Changes in activities and participation since COVID-19 questionnaire

In the next set of questions, we will ask you about how your perceived functional ability and daily activities have changed since social distancing began due to COVID-19. You can reply by the following 5-point scale: much worse, a little bit worse, stayed about the same, a little bit better, much better.

Activities	Much Worse	A little bit worse	About the same	A little better	Much better
Your ability to move around in your home (such as walking, climbing stairs) become ...					
Your ability to engage in sports or recreational activity (such as casual/brisk walking, dancing, bowling, shuffleboard, hiking, Yoga, gymnastics, stationary bike,) become ...					
Your ability to engage in housework activity (such as dusting, washing dishes, and vacuuming) become ...					
Your ability to stay physically active (walking, exercise, working out) become..					
Participation	Much Worse	A little bit worse	About the same	A little better	Much better
Since social distancing began due to COVID-19 has ...					
Your ability to keep in touch with others (through letters, cell phone/phone or email) become ...					
Your ability to take care of your health (such as managing daily medications, following a diet, cooking your own meals, bathing, dressing and toileting) become ...					
Your ability to take care of your errands (such as buying groceries or taking care of finances) become ...					
Your ability to participate in the community and maintain a social life (e.g., volunteer, go to church, meet with others) become...					

REFERENCES

3. Neuro VI. Perioperative covert stroke in patients undergoing non-cardiac surgery (NeuroVISION): a prospective cohort study. *Lancet* 2019;394(10203):1022-29. doi: 10.1016/S0140-6736(19)31795-7

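### The activities questionnaire is read as showing deferral impact on the premise that deferral coincided with the start of social distancing; later deferrals are eligible and the deferral date is not a listed data item

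*Combined protocol and SAP*

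**What the plan says.** Section 2 sets a secondary objective of comparing participants' change in activities and participation with that of a community sample aged 65 or older, "in order to identify the additional impact of surgery deferral". Section 3.4.2 says that "the questionnaire will be administered by the research personnel only once, i.e. at baseline", and that the onset of social distancing is an event "which, for the participants in our study temporally coincided with the change to their surgical plan". Each Appendix III item is anchored to that onset: respondents are asked "how your perceived functional ability and daily activities have changed since social distancing began due to COVID-19".

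Other sections bear on when deferral can happen:
- Section 3.2 describes patients "whose surgery has been or will be deferred due to the slowdown of the operating rooms during the COVID-19 emergency".
- Section 3.2.1 requires "surgery deferred, with a known or probable surgery date in ≥6 weeks", with no limit on when the deferral was decided.
- Section 3.5 states: "The slowdown of the operating rooms due to COVID-19 started in mid-March, and it will last at least until the end of June or July". It plans recruitment from May to August 2020 and expects the restrictions to carry over to at least the end of summer. If recruitment is slow, "we will extend our recruitment period to beyond the summer".

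Section 3.4 lists the date and type of surgery among the data to be obtained. Neither it nor Appendix I lists the date of deferral. Section 3.6.2 does not describe the community comparison, and so has no analysis by time since deferral.

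**The concern.** Reading the patient-versus-community difference as the effect of deferral is simplest if deferral and distancing began together. The whole recall period is then a period of deferral, and time since deferral can be read off the interview date. Section 3.4.2 asserts this for the participants without qualification, but the recruitment and eligibility text allows participants for whom it is untrue.

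For those participants the questionnaire starts counting before the exposure does. Two things follow. A surgical candidate may already have drifted away from community respondents before deferral, for example through the condition that led to the planned operation, and that drift would be labelled deferral impact. In addition, the group difference mixes patients who have lived with deferral for months with patients who have lived with it for weeks, in unrecorded proportions. A small difference could mean little impact, or little time for impact to appear, and the listed data would not tell the two apart.

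**Working it through.** The plan gives no sample size, effect size or timing figure for this objective, so there is no stated number to reproduce. The 330 of section 3.5 rests on the One-Back Task and is not involved.

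**1. Can deferral come well after distancing began?** Section 3.5 puts the start of the operating-room slowdown in mid-March. The protocol is dated 31 May 2020. Counting from 15 March, that is 77 days, or 11 weeks. A patient whose surgery had yet to be deferred at the protocol date would be deferred at least 11 weeks after the slowdown began. The statement in 3.4.2 can therefore hold for only part of the eligible population.

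**2. How much of the recall period can precede deferral?** The documents do not date the start of social distancing, so 15 March is an assumption taken from the slowdown. With d = days from 15 March to deferral and q = days from 15 March to interview, the part before deferral is d/q and the time since deferral is q − d.

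| Deferred | Interviewed | d/q | Days since deferral |
|---|---|---|---|
| 15 March | any date | 0% | q |
| 1 June | 30 June | 78/107 = 73% | 29 |
| 1 June | 31 August | 78/169 = 46% | 91 |
| 1 July | 31 July | 108/138 = 78% | 30 |
| 1 August | 31 August | 139/169 = 82% | 30 |

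These are possible cases within the planned recruitment window, not estimates of what is typical.

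**3. What enters the comparison?** Write a patient's reported change as C + B(d) + I(q − d). C is distancing-related change shared with the community. B(d) is any divergence of surgical candidates from the community between the start of distancing and deferral. I(q − d) is the impact of deferral accrued by the interview. The community response is C. The difference is B(d) + I(q − d).
- C cancels, because both groups use the same anchor.
- B(d) is zero when d = 0. Otherwise it is of unknown sign and size, and is read as deferral impact.
- I depends on q − d, which is not recorded.

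Divergence after deferral for other reasons concerns the comparability of the groups and is outside this point.

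**4. How many patients could be affected?** The documents do not say. As an illustration, the share deferred more than 60 days after 15 March is:
- all deferred in mid-March: 0%;
- 90% in the first 30 days, the rest evenly to 30 June (day 107): 0.10 × (107 − 60)/(107 − 30) = 6%;
- 80% in the first 30 days, the rest evenly to 30 June: 0.20 × 47/77 = 12%;
- evenly from mid-March to 30 June: 47/107 = 44%;
- evenly from mid-March to 31 July (day 138): 78/138 = 57%.

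The range of 0% to 57% comes entirely from the assumed deferral dates.

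**The case against.** The case on the other side is substantial, and most of it stands.

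- A reader might infer that the reference period is defined in two incompatible ways. It is not: 3.4.2 and Appendix III both use the start of distancing. The coincidence clause is a remark about timing. A common anchor is needed, since community respondents have no deferral date.
- A reader might infer that distancing-related change before deferral is counted as deferral impact. The part shared by both groups cancels. Only divergence between the groups remains.
- A reader might treat the share of the window after deferral as a dilution factor. If deferrals are spread evenly to the end of June or July, and interviews evenly from the later of 1 May or deferral to 31 August, the mean share is 53% or 44%, which suggests an effect roughly halved. This does not follow. The items compare the present with the time before distancing and do not average over the window, so a recently deferred patient reports all the impact accrued so far. A smaller impact after a shorter wait is shorter exposure. The even spread is also unsupported: with 80% of deferrals in the first 30 days and the rest by 30 June, the mean share is 75%.
- A reader might take recruitment beyond the summer as deferral beyond the summer. The extension is conditional, and section 3.5 cites a median of 45 weeks to clear the backlog, so a late recruit may have been deferred in March.
- A reader might conclude that the deferral date is lost. It is unlisted, not shown to be unrecoverable: deferral must be established for eligibility, surgical practices are in periodic contact, records are reviewed, and the baseline list in 3.4 is open-ended.

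None of this rescues the unqualified sentence in 3.4.2, supplies the missing date, or adds an analysis that takes account of it.

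**Conclusion.** The concern holds in a limited form. The coincidence stated in 3.4.2 is not guaranteed by the plan's own recruitment and eligibility text. For patients deferred later, the reading given in section 2 can absorb pre-deferral divergence, and it averages over times since deferral that the plan does not list for collection.

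The size cannot be stated from the documents. It is nil if every participant was deferred in mid-March, and larger if deferrals continued through June or July. The calendar cases rest on 15 March as the start of distancing and show what is possible for individual patients; they measure neither bias nor dilution. That surgical candidates diverge from the community before deferral is plausible but not documented.

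One descriptive secondary objective, which the study summary does not list, is affected. The primary analysis and the sample size are not.

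**What to change.** 1. At the initial videoconference, record the date on which surgery was deferred and the original surgery date. Add both to section 3.4 and Appendix I.
2. In 3.4.2, replace the statement of coincidence with one saying that deferral may have followed the start of distancing by a varying interval.
3. In 3.6.2, describe the community comparison and report it by time from deferral to interview. Add a sensitivity analysis limited to patients deferred near the start of distancing, with the cut-off fixed before the data are examined. Making that restriction the main analysis would discard data and is a trade-off, not a necessity.

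The cost is one or two date fields, a few lines of text, and lower precision in the sensitivity subset. No extra visits or patients are needed. The fields are best added early in recruitment, since dates not taken at baseline are harder to recover. If the dates show that nearly everyone was deferred in March, the sponsor can say so and the point closes.
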